Based on medical chart review, all patients will first be screened for eligibility. Patients will only be enrolled in the study if they meet both inclusion and exclusion criteria. The study will be explained to the patient and informed consent will be obtained before they undergo baseline social and cognitive assessments and receive a laptop to begin either a social-cognitive or control training condition (randomly determined by selecting one of 30 sealed envelopes).

Following the completion of the 20-30 hours of training over the course of 4 weeks, the patient will be assessed with the same measurements again. The patient will then complete the second training condition (20-30 hours over 4 weeks) that they were not randomly assigned to initially. The patient will then receive a final assessment, return the laptop, and receive compensation for the study.

Each of the three assessments will include the following tests: 1) Star Cancellation test, an assessment of spatial attention (Friedman, 1992); 2) Interpersonal Reactivity Index (IRI), a subjective evaluation of 4 components of empathy, rated by the caregiver (Davis, 1983); 3) Reading the Mind in the Eyes Test (RMET), an objective evaluation of empathy (Baron-Cohen

et al., 2001); 4) Social Cognitive Tasks from the University of Pennsylvania Computerized Neurocognitive Battery (Penn CNB), a measure of affect perception and facial memory (Gur et al., 2010); 5) Prosody Battery, a well-validated test of expression and production of prosody (Ross and Monnot, 2008; Ross et al., 1997); 6) Forward and Backward Digit Span, a brief assessment of attention and working memory; 7) Faux Pas Test, a test of social awareness (Gregory et al., 2002); and 8) the Patient Health Questionnaire-9, a well-validated screening tool for depression (Kroenke et al., 2001). The IRI must be completed by a caregiver or spouse.

b. Study duration and number of study visits required of research participants.

The study duration is around 8 weeks for each participant and will require 3 total participant visits for the baseline, 1st post-treatment (1st condition), and 2nd post-treatment (2nd condition) assessments. If there are technical issues with the laptop or online portal, assistance will be provided remotely if possible.

c. Blinding, including justification for blinding or not blinding the trial, if applicable.

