- c. Justification and safety information if non-FDA approved drugs without an IND will be administered. N/A

7. Study Statistics

- a. Primary outcome variable.

Change in performance from baseline to 1st post treatment on Penn CNB tasks (Total) vs. 1st post-treatment (new baseline) to 2nd post-treatment on Penn CNB tasks (total).

- b. Secondary outcome variables.

Changes in total and subtest scores on IRI, Prosody Battery, RMET, Faux Pas Test, and star cancellation.

- c. Statistical plan including sample size justification and interim data analysis.

We will compare the change in means of outcome measures after social cognition treatment vs. control treatment. The primary outcome variable will be change in performance on the Penn CNB tasks after the end of each treatment. The null hypothesis is $H_0: \mu_1 = \mu_2$, where μ_1 is the mean change in performance on the Penn CNB tasks between pre-treatment and post-treatment with social cognition treatment and μ_2 is the mean performance on the Penn CNB tasks between pre-treatment and post-treatment with control treatment.

Analyses. In a cross-over trial, it is essential to evaluate the effect of condition versus the effect of sequence of the treatment, and to evaluate for carry-over from one treatment to the next. Based on our clinical experience we expect little change in the Penn CNB with the control (non-specific cognitive exercises) in chronic right hemisphere stroke (as we see decline rather than recovery in chronic stroke in these functions), and little change or decline in patients with behavioral variant FTD. But we will evaluate the effect of condition versus sequence independently. The primary analyses will evaluate the change in performance on Penn CNB as the dependent variable, $Y_{ij} = \mu + S_i + \mu_{(j)} + C_{(j)} + e_{ij}$ where i represents a subjects, j represents the sequence (1 or 2). The Y_{ij} is the change in the evaluations. The S_i represents the random effect of the subjects. The $\mu_{(j)}$ represents the means of the two treatments (social cognition or control). The $C_{(j)}$ represents the carryover effects. The test for the treatment effect can be obtained from this model. Firstly, the effect of carryover effects will be tested at $p < 0.1$. If this is significant, then only the first sequence data will be analyzed as this sequence is free of carryover effects. A similar analysis will be done for the change in accuracy of secondary outcome variables.

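### The first-period fallback analysis compares raw Penn CNB change in about 13 v 13 patients and leaves out the baseline score as a covariate

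*Combined protocol and SAP*

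**What the plan says.** Section 7a defines the primary outcome as change in the Penn CNB total over each training period. The second change is measured from the 1st post-treatment assessment. Section 7c repeats this: "The primary outcome variable will be change in performance on the Penn CNB tasks after the end of each treatment", and "The primary analyses will evaluate the change in performance on Penn CNB as the dependent variable". The model holds an overall mean, a random subject effect, treatment, carryover and error. Neither 7c nor any other section names a baseline covariate.

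Carryover is tested first, at the 0.1 level. The plan then says: "If this is significant, then only the first sequence data will be analyzed as this sequence is free of carryover effects". Section 7c uses its sequence index (1 or 2) for the two training periods, so I read this as the first period. Only that reading leaves a treatment comparison to make. No other outcome is given for this fallback, so the change score carries over to it. Section 7c promises a similar analysis for the secondary outcomes.

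Baseline scores will be available, since section 4a says "informed consent will be obtained before they undergo baseline social and cognitive assessments" and places delivery of the laptop after that. The sealed-envelope draw appears in the same sentence, but the text does not say whether it comes before or after baseline testing.

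Section 7c (Power) expects 20 to 30 completers. It claims 86% power with 13 per group for a difference of 6 (10 v 4) at two-sided 0.05. It states no standard deviation and no between-visit correlation.

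**The concern.** A raw change score fixes the weight on baseline at one. The efficient weight is the regression slope of the later score on baseline, which equals r when the two visits have equal variance. If r is well below 1, subtracting the whole baseline adds noise.

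In the fallback this noise does not cancel within patients, because the comparison is between two small groups. With 13 per group, the standard error of a chance baseline difference is √(2/13) = 0.39 SD. A change score passes a fraction (1−r) of such a difference into the estimate. For a one-standard-error imbalance that is 0.3 × 0.39 = 0.12 SD at r=0.7 and 0.5 × 0.39 = 0.20 SD at r=0.5. A baseline covariate removes it.

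Precision is at stake, in the analysis where the trial can least afford to lose it. Validity is not at stake.

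**Working it through.** **The plan's own figure.** The 86% cannot be reproduced forward because no SD is stated. Solving backwards for a two-group comparison of 13 v 13 and a difference of 6, the SD that gives 86% is 5.03 (normal approximation) or 4.83 (noncentral t, 24 df). At a round SD of 5, power is 86.4% (normal) or 83.5% (noncentral t). I use SD 5 and the noncentral t below; the SD is an assumption.

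**First-period comparison.** Assume equal variance σ² at each visit and correlation r.
- Change score: variance per patient = 2(1−r)σ².
- Baseline as covariate: residual variance = (1−r²)σ².
- Ratio = (1−r²) / [2(1−r)] = (1+r)/2.
- Cost of estimating the slope: factor 1 + 1/(N−4). At N=26 this is 1 + 1/22 = 1.045.
- Net ratio = (1+r)/2 × 1.045.

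| r | (1+r)/2 | Net ratio, N=26 | Power, change score | Power, baseline covariate |
|---|---|---|---|---|
| 0.5 | 0.750 | 0.784 | 83.5% | 91.1% |
| 0.7 | 0.850 | 0.889 | 83.5% | 87.4% |
| 0.8 | 0.900 | 0.941 | 83.5% | 85.5% |
| 0.9 | 0.950 | 0.993 | 83.5% | 83.6% |
| 0.95 | 0.975 | 1.019 | 83.5% | 82.7% |

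The net ratio reaches 1 at r = 2 × 22/23 − 1 = 0.91.

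In patients: 26/0.784 = 33.2, about 7 more than 26; 26/0.889 = 29.2, about 3 more; 26/0.941 = 27.6, between 1 and 2 more; at r=0.9, none to speak of.

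Simulation (20,000 trials per r, 13 per group) gave variances of the estimated difference, change score then covariate, of 3.81 and 2.96 (r=0.5), 3.85 and 3.43 (0.7), 3.88 and 3.62 (0.8), and 3.79 and 3.78 (0.9). The ratios are 0.78, 0.89, 0.93 and 1.00.

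Across the expected number of completers, the net ratio at r=0.5, 0.7, 0.8 and 0.9 is 0.797, 0.903, 0.956 and 1.009 at N=20, and 0.779, 0.883, 0.935 and 0.987 at N=30.

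**If the 86% belongs to the crossover contrast instead.** The implied root mean square error is 6.83 and the SD of the within-person contrast is √2 × 6.83 = 9.65. Under equal correlations the SD of a single change is 9.65/√3 = 5.57. First-period power is then 75.0% on raw change, against 84.3%, 79.6%, 77.3% and 75.1% with the covariate at r=0.5, 0.7, 0.8 and 0.9. The variance ratios do not change.

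**Pooled crossover contrast, for comparison.** First change minus second change = 2·post1 − baseline − post2.
- Equal correlations: variance 6(1−r)σ², covariance with baseline −(1−r)σ², ratio after adjustment 1 − (1−r)/6. Times 1.045 at N=26: 0.958 (r=0.5), 0.993 (0.7), 1.011 (0.8), 1.028 (0.9).
- Correlation decaying with time (r between adjacent visits, r² across two): simulated ratios at N=26 of 1.016, 1.035, 1.044 and 1.045 at the same r.
- At N=20 the simulated range over both structures is 0.972 to 1.064. At N=30 the best case is 0.917 × (1 + 1/26) = 0.952.

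**The case against.** The strongest reply is that this concerns an analysis that may never be run. If there is no carryover and the test holds its level, the fallback is used about one time in ten. That stands, and it limits the importance of the point. It does not remove it: carryover would make the fallback more frequent, and the plan describes no wash-out.

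A second reply is that raw change is valid under randomisation. Chance imbalance adds variance, not bias, and no type I error problem follows. That also stands; the argument is about efficiency only.

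A third is that the gain rests on an unknown r. This is true, and it is why the range matters. The gain is worthwhile up to about r=0.8, negligible at 0.9, and a loss of about 2% at 0.95.

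A reader might infer more: that the primary analysis as a whole wastes precision for no return. The documents do not support that. The primary analysis is the pooled crossover model, where the within-person contrast has already removed most of what baseline could explain. Once the slope is estimated, adjustment there ranges from a gain of about 4% at 26 completers (just under 5% at 30) to a loss of about 6% at 20. Moreover, adding baseline as a main effect to the stated random-subject model leaves the within-person contrast unchanged. A baseline-by-period term would be needed for even the small gain.

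A reader might also quote variance cuts of 25% and 15% at r=0.5 and 0.7. Those figures treat the slope as known; net of its cost they are 22% and 11%.

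**Conclusion.** The point holds for the first-period fallback and for nothing wider. Section 7c would compare raw change between two groups of about 13 and leave a baseline score that every patient has already supplied out of the model. Using it as a covariate is at least as precise for any r up to about 0.9 at 26 completers, and clearly better at 0.5 to 0.7. The sizes rest on equal variances at the two visits and on assumed correlations; the power figures also rest on an assumed SD. It would be wrong to say that baseline is ignored: the first-period change subtracts it, and what is missing is its use as a covariate. This is a worthwhile, low-cost improvement to a contingent analysis.

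**What to change.** In section 7c, state that any analysis restricted to the first period will regress the 1st post-treatment Penn CNB total on condition, with baseline Penn CNB total as a covariate, in place of the raw change score. State the same for each secondary outcome with its own baseline. Say in section 4a that the envelope is drawn after baseline testing, so that the covariate is plainly measured before randomisation. In the power paragraph, give the SD and any between-visit correlation behind the 86%.

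Leave the pooled crossover model without a baseline term.

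The cost is one degree of freedom in the fallback analysis and a few sentences of text. No new data, visits or patients are needed. The wording should be fixed before any outcome data are examined by condition.

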1. Test the hypothesis that patients with right hemisphere stroke and frontotemporal dementia (FTD) show more improvement on untrained tests of social cognition after web-based social-cognitive training exercises (Posit Science Inc.) than after non-specific cognitive training.
2. Evaluate patients with FTD and stroke in multiple domains of social cognition (such as emotional contagion, affective perspective-taking, and affective prosody identification) as well as mood, attention, and working memory, before and after intervention to identify which functions improve after training.
3. Assess the feasibility and acceptability of web-based interventions in patients with stroke or FTD through examination of usage data and patient feedback.
4. Determine the effects of location of lesion or focal atrophy on improvements in social-cognitive training exercises with intervention.

3. Background (briefly describe pre-clinical and clinical data, current experience with procedures, drug or device, and any other relevant information to justify the research)

Problem: Both patients with stroke or FTD can experience impairments in social-emotional functioning. While the profile of deficits may differ in these two illnesses, there are convergent issues in empathic abilities especially in right hemisphere stroke and behavioral variant FTD. Deficits or deterioration in empathy can impact patients' interpersonal relationships and adversely impact patients' quality of life. However, there are currently very few treatments that specifically target these issues, and many of them are limited in their scope and effectiveness. Recently, web-based training interventions have shown efficacy in treating functional impairments in stroke and social deficits in other disorders such as schizophrenia. It is crucial to test whether this cost-effective and mobile intervention can be effectively utilized to treat social-emotional deficits in patients with stroke or FTD.

4. Study Procedures

- a. Study design, including the sequence and timing of study procedures (distinguish research procedures from those that are part of routine care).

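### The primary crossover model in section 7c has no term identified as a period effect, so how a period difference is handled depends on how the carryover term is read

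*Combined protocol and SAP*

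**What the plan says.** The Analyses paragraph of section 7c states that in a crossover "it is essential to evaluate the effect of condition versus the effect of sequence of the treatment, and to evaluate for carry-over", and later promises: "But we will evaluate the effect of condition versus sequence independently".

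The model that follows is `Y_ij = μ + S_i + μ_(j) + C_(j) + e_ij`, "where i represents a subjects, j represents the sequence (1 or 2"). Y is the change over one training condition. S_i "represents the random effect of the subjects", μ_(j) holds the two treatment means, and C_(j) "represents the carryover effects. The test for the treatment effect can be obtained from this model".

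Carryover is tested first, at p<0.1. "If this is significant, then only the first sequence data will be analyzed as this sequence is free of carryover effects". Here 'sequence' can only mean the first condition received, which is a period and not an order.

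Section 7a words the primary outcome by period: "Change in performance from baseline to 1st post treatment on Penn CNB tasks (Total) vs. 1st post-treatment (new baseline) to 2nd post-treatment". Objective 1 in section 2 words it by condition: patients should "show more improvement on untrained tests of social cognition after web-based social-cognitive training exercises" than after the control training. The null hypothesis in 7c is also worded by condition.

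Section 4a repeats the same measurements at each of the three assessments and describes no washout between conditions. Section 7d restricts Aim 1 to patients who complete the whole study.

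**The concern.** In a two-period crossover the usual primary model has subject, period and treatment. Here the only index besides subject is j, and both treatment and carryover sit on it. Nothing in the equation or in the list of its terms is called a period or order effect.

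A period difference is plausible because the tests are repeated. A practice gain, for example, may be larger between the first and second assessments than between the second and third. Steady decline or steady gain would not produce one, because Y is measured from a new baseline in each period.

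The primary estimate, and whether half the data are discarded, should not depend on how an analyst chooses to read C_(j).

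**Working it through.** **Inputs from the documents.** Section 7c, Power: 13 per group, 26 in total; difference 6 (10 versus 4); two-sided alpha 0.05; 86% power. Section 7c, Analyses: carryover test at 0.10.

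**Assumptions.** True effect T = 6; period-1 minus period-2 change P = 4; no true carryover; 13 completers per order; the two changes of a patient uncorrelated (r = 0).

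**The plan's own figure.** No SD is given, so 86% cannot be reproduced, only inverted (noncentral t, 24 df).
- Reading 1, crossover test on within-patient differences: solving for power 0.86 with noncentrality 6/(SD/√26) gives a difference SD of 9.65.
- Reading 2, ordinary two-group test: solving with noncentrality 6/(SD·√(2/13)) gives an SD of change of 4.83, so a difference SD of 4.83·√2 = 6.83.

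**Is period really absent?** The design has four cell means (two orders by two periods). Mean, treatment and one carryover column for social-cognition training span three of them; adding period makes four. So period is an omitted effect under that reading. A further sequence column adds nothing: order and carryover are aliased.

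**Cell means without carryover.** Social-cognition first: T+P, then 0. Control first: P, then T.

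**(A) C dropped.** The within-patient difference (social-cognition minus control) averages T+P in one order and T−P in the other. Without a period term this spread goes into the error.
- Power by simulation (40,000 trials): 82% against 86% (SD 9.65), and 98% against 99% (SD 6.83).
- Bias = P × (difference in order sizes)/(total). It is 0 at 13:13, 4 × 4/26 = 0.6 points at 15:11, and 4 × 6/26 = 0.9 points at 16:10.

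**(B) C indexed by period.** C then equals the period effect, so treatment is period-adjusted while C is kept. But C is tested as carryover. Its noncentrality is P/(SD/√26):
- 4/(9.65/√26) = 4/1.893 = 2.11, which rejects at 0.10 in 66% of trials;
- 4/(6.83/√26) = 4/1.339 = 2.99, which rejects in 90%.

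With P = 2 the figures are 27% and 42%. Power over the whole rule at P = 4 is about 67% (reading 1) or 87% (reading 2).

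**(C) C is carryover of social-cognition training into period 2.** C takes up the whole cell 'control after social-cognition'. At r = 0 treatment is then estimated from the other three cells:
- treatment = [(T+P) + T]/2 − P = T − P/2 = 6 − 2 = 4;
- false carryover = 0 − P = −4.

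The carryover test fires in 42% (reading 1) or about 65% (reading 2) of trials. When it fires, the analysis moves to period-1 data, where both orders share the same period and the bias disappears. Over the whole rule the bias is −1.2 or −0.7 points if a non-significant C stays in the model, and −0.5 or −0.4 if it is then dropped.

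**Adding period.** Without C, treatment is half the between-order difference in (period-1 change minus period-2 change): [(T+P) − (P−T)]/2 = T, whatever P is. Power is 86.0%, 85.2% and 84.1% at 13:13, 15:11 and 16:10 (SD 9.65), and about 99% at all three (SD 6.83). With C also kept, all four cells are used up and treatment becomes the period-1-only contrast. Compared with model C without period, at P = 0, power falls from 0.72 to about 0.59 (reading 1) or from 0.95 to about 0.87 (reading 2).

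**The case against.** **C_(j) may already be a period term.** If j means period, C_(j) is literally period-indexed and adjusts the treatment estimate. This stands for reading (B), but there the term carries the wrong name and drives a rule that discards data.

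**Order is aliased with carryover, so C_(j) covers 'sequence' in the strict sense.** True in this design. But that supplies no period effect, and sequence and carryover then cannot be evaluated as separate things.

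**The two-group t-test in the Power paragraph may remove period.** It would, if it compares within-patient differences between the two orders; reading 1 assumes exactly that test. But it appears only in the power statement, its grouping is by treatment and not by order, and the Analyses paragraph takes the treatment test from the model. The two need to agree.

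**Stronger inferences the documents do not support.**
- That a period difference badly biases the result. Under (A) with equal orders there is no bias and little loss of power. Under (C) the pre-test rule reduces the 2-point error, and whole-rule type I error stays near 5%.
- That the error under (C) reaches 3 or 4 points. That needs a correlation of 0.5 or a purely within-patient fit. The plan states a random subject effect, and the two changes share the middle assessment with opposite sign, which pulls their correlation down.
- That a period term alone cures everything at almost no cost. This holds only if C also leaves the primary model.
- That 7a commits the trial to testing period 1 against period 2. Objective 1 and the null hypothesis settle that the contrast is between conditions.

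**Conclusion.** The point holds as a fault of specification: what the plan calls essential is not identifiable from its primary equation. That conclusion needs no SD.

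The size of the harm is conditional. It rests on an assumed 4-point period difference, uncorrelated changes, and SDs inferred from the power statement. On those assumptions it runs from a modest loss of power (A), through needless discarding of second-period data in 66% or 90% of trials (B), to an understated treatment effect (C). Much of the harm under (B) comes from the discard rule acting on a mislabelled period effect, not from the missing term alone. If the second-period change were the larger one, the bias under (C) would be upward.

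The plan should be changed, but nothing here shows that the trial's conclusion would be invalid.

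**What to change.** - Fit `Y_ij = μ + S_i + period_j + treatment_d(i,j) + e_ij` as the primary and secondary model, where j is the period and d(i,j) the condition patient i had in that period.
- Index treatment, period and order separately. Use 'period' for first or second condition and 'sequence' for the order of conditions.
- Take carryover out of the primary model. Report the order (carryover) test separately, without letting it choose the analysis, and report the period-1-only comparison as a sensitivity analysis whatever that test shows.
- Make the test in the Power paragraph the one this model gives.
- Reword 7a as change on the Penn CNB total over social-cognition training minus change over control training.

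**Cost.** Some rewording, one degree of freedom, and the slight precision loss shown above if orders finish unequal. The real downside is carryover. If social-cognition training adds L points to the change in the following control period, the model estimates T − L/2, so 4 points of carryover shift the estimate by 2. The effect is overstated if gains fade during control training and understated if they keep growing. Since no washout is described, this should be stated as a limitation.

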Power. We expect to enroll up to 50 patients in the study, and expect 20-30 participants will complete the study. Because of the social cognitive deficits in these patients (accompanied by relatively low insight and motivation), there is likely to be high attrition. If the sample size in each treatment group is 13, (a total sample size of 26) a crossover design will have 86% power to detect a difference in means of 6 (the difference between treatment mean change in accuracy, μ_1 , of 10 and a control mean change in accuracy, μ_2 , of 4) using a two group t -test with a two-sided alpha of 0.05.

- d. Early stopping rules.

Patients will be allowed to stop at any time, but they will not receive compensation if they fail to complete all criteria for compensation. Their data will only be used for Aim 1 if they complete the entire study. We may be able to use data from participants who complete the social-cognition treatment condition only for Aims 2 and 3.

8. Risks

- a. Medical risks, listing all procedures, their major and minor risks and expected frequency. There are no known risks associated with the training software, use of a laptop computer, or the assessments used in this study. Participants could become bored, anxious, or embarrassed during assessment of cognitive function.
- b. Steps taken to minimize the risks. The participant will be able to stop participation at any time if they experience any issues with the use of the training software or assessments of social abilities.
- c. Plan for reporting unanticipated problems or study deviations. The PI will report unanticipated problems or study deviations to the IRB immediately.

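### The primary crossover model leaves the fit and the period effect open; fitted as a usual mixed model, with carryover dropped or coded as sequence, its nominal 5% treatment test can run at up to about 10-11%

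*Combined protocol and SAP*

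**What the plan says.** Section 4a sets three assessments. After the first training block, "the patient will be assessed with the same measurements again", and a final assessment follows the second block. Section 7a defines the primary outcome as "Change in performance from baseline to 1st post treatment on Penn CNB tasks (Total) vs. 1st post-treatment (new baseline) to 2nd post-treatment" on the same test total.

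Section 7c takes these changes as the dependent variable: "The Y_{ij} is the change in the evaluations. The S_i represents the random effect of the subjects". The fixed terms are a treatment mean and a carryover term, both indexed by j, where "j represents the sequence (1 or 2"). There is no period term. Of the primary comparison it says "The test for the treatment effect can be obtained from this model". Carryover is tested first at 0.10: "If this is significant, then only the first sequence data will be analyzed as this sequence is free of carryover effects". The approach extends to the other endpoints: "A similar analysis will be done for the change in accuracy of secondary outcome variables".

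The power paragraph of 7c names a different procedure, a two-group t-test at a two-sided 5% level. It assumes 13 per group and a difference of 6 (10 against 4), for 86% power. It adds that the investigators "expect 20-30 participants will complete the study". Section 7d restricts Aim 1 to people who finish the whole study.

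The documents state no estimator, degrees of freedom, variance constraint, correlation or standard deviation.

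**The concern.** The first post-treatment score enters the first change with a plus sign and the second with a minus sign. Error in that one score makes the first change look larger and the second smaller, so it pulls their correlation down. A random subject effect whose variance cannot go below zero can represent only a zero or positive correlation. If the true correlation is negative, such a fit goes to the boundary, pools between- and within-person variation, and understates the standard error of the within-person treatment contrast.

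The missing period term is a second, separate gap. Practice on a repeated test, or decline over the two blocks, would go into the residual. If unequal numbers complete the two orders, it would also go into the treatment estimate.

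At stake are the error rate and confidence interval of the test of objective 1 and, by extension, of the secondary outcomes.

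**Working it through.** **Power figure first.** No SD is given, so the 86% cannot be reproduced, only back-solved. With 24 df and SE = SD × sqrt(2/13), where SD is that of half the within-person difference, 86% needs SD = 4.83 (9.65 for the full difference). Check: 4.83 × 0.392 = 1.89; 6/1.89 = 3.17; the noncentral t gives 86%. The figure is plausible but unverifiable. Nothing below depends on it.

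**Correlation of the two changes (assumed; not in the documents).** Let the three scores have common variance s² and common correlation r. Each change has variance 2s²(1 - r) and their covariance is -s²(1 - r), so the correlation is -0.5. If patients also differ in rate of change, with slope variance b and independent visit errors of variance v, the correlation is (b - v)/(b + 2v):
- b = 0 gives -0.5
- b = 0.5v gives -0.5/2.5 = -0.20
- b = v gives 0
- larger b gives a positive value

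The range examined is +0.2 to -0.5.

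**Large-sample size of the effect.** With the subject variance at zero, the fitted SE is 1/sqrt(1 - rho) times the true SE. The error is 2 × [1 - Phi(1.96/sqrt(1 - rho))].
- rho = -0.5: SE ratio 0.816, error 10.95%
- rho = -0.20: SE ratio 0.913, error 7.36%

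**Simulation at the planned size.** 13 completers per order, normal data, no true effect, 100,000 trials per setting, REML with subject variance not below zero, carryover dropped, no period effect or a period term fitted. Error ranges cover t references from 24 to 50 df and the small differences between repeat runs.

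| Correlation | Subject variance at zero | Fitted/true SE | Error, bounded mixed model | Error, two-group t-test |
|---|---|---|---|---|
| +0.2 | 16% | 0.989 | 5.0-5.7% | about 5% |
| 0 | 50% | 0.959 | 5.5-6.4% | about 5% |
| -0.20 | 84% | 0.904 | 6.9-7.8% | about 5% |
| -0.5 | 99.5% | 0.812 | 10-11% | about 5% |

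There is a small excess at correlation 0 because the constraint pools the variances only when pooling lowers the estimate. Keeping carryover as a sequence effect changes little (9.9-11.0% at -0.5). With 20 or 30 completers the rate at -0.5 is 9.8-11.1% or 10.2-11.1%.

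**Fits that do not inflate.**
- Within-subject ANOVA of the printed model, no period effect: 5.0-5.1%.
- Unstructured covariance with period and sequence terms on 24 df: same t statistic as the two-group t-test. Without the sequence term it ran at 6.0-6.4%.
- Carryover kept as a lagged-treatment term: 4.3-5.2%.

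**Period effect present but not fitted** (assumed size: 1 SD of a change; carryover dropped).
- Equal orders: the ANOVA runs at about 2% (1.7% at correlation 0, 2.5% at -0.5). The bounded model runs at 2.5-3.0% at 0 and 6.6-7.4% at -0.5.
- Unequal orders, assumed 16 and 10: the treatment estimate is biased by (16 - 10)/26 = 0.23 SD. The ANOVA runs at about 6%. The bounded model runs at 8.2-9.2% at 0 and 12.8-14.0% at -0.5.
- The two-group t-test between orders stays at about 5% in both cases.

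**Whole two-step rule, no true carryover.** With the t-test in second place: 5.8% at -0.5, 6.4-6.6% at -0.20, 6.7-6.9% at 0. With the bounded model plus a period term: 10.5-11.4%, 8.2-9.0% and 7.3-8.1%.

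**The case against.** The strongest reply is that the plan never commits to the fit that inflates. Section 7c prints a model, not an estimator, and the same terms can be tested as an ordinary crossover ANOVA against the within-subject residual, which holds about 5% when there is no period effect. The power paragraph even names a two-group t-test, so the right test may already be intended. This stands. A reader might infer that the primary test does run at 6-11%. The documents do not support that, because the figure needs a non-negative variance constraint that they do not state.

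Carryover coding matters too. Section 7c speaks of carryover from one treatment to the next, which suggests a lagged-treatment term, and keeping such a term removes the inflation. Against that, j is defined as sequence. With a lagged term always in the model the treatment contrast would already rest on the first period, so the planned fallback to first-period data would serve no purpose. The text leaves both readings open.

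The value -0.5 is an extreme. It allows no differences between patients in rate of change, and the sample mixes stroke with a progressive dementia. At zero or positive correlation the excess is a point or less.

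Finally, the t-test is not immune. With an assumed SD ratio of 1.5 between orders and a 16/10 split, the pooled version ran at 3.4% or 7.4%, depending on which order was more variable.

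**Conclusion.** The concern holds as a conditional one: the error rate of the primary treatment test depends on choices that section 7c does not make. The 5-6% to 10-11% range across correlations +0.2 to -0.5 assumes a subject variance not below zero, carryover dropped or coded as sequence, no period effect or a fitted one, normal data and 13 completers per order. Change the fit to a within-subject ANOVA, an unbounded covariance with period and sequence terms, or a retained lagged carryover term, and this inflation is gone.

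The missing period term is a separate weakness that also affects the ANOVA reading. It costs sensitivity with equal orders and biases the estimate with unequal ones. Unequal orders are realistic given the attrition that the plan itself expects, but the 1 SD period effect and the 16/10 split are illustrations, not document figures.

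A reader might also infer that the recommended t-test brings the planned procedure to 5%. It does not: the 5% is for that test alone, with equal variances, and the 0.10 carryover pre-test keeps the two-step rule at about 6-7%. No revised power is claimed. This should be fixed; confidence is medium because the correlation and the intended fit are unknown.

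**What to change.** In section 7c, name the primary treatment test: a two-group t-test between the two orders on each completer's (period-1 change minus period-2 change)/2, and use it for the secondary outcomes. This removes any period effect, does not depend on the correlation, suits the completers-only set for Aim 1, and agrees with the test in the power paragraph. A Welch version relaxes the equal-variance assumption.

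If a mixed model is preferred, specify period and sequence terms, an unstructured or unbounded covariance, and small-sample degrees of freedom (24 with 26 completers). With complete data this reproduces the t-test. In either case, state which SD gave the 86% power.

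The cost is a sentence or two and no new data. When the correlation is negative, the standard error will be larger than the bounded model's: about 23% at -0.5 (1/0.812) and 11% at -0.20 (1/0.904). The excess from the carryover pre-test is a separate matter that this change leaves in place.
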